5.1. Inclusion Criteria

Patients with UC will be included in the study only if they meet all of the following inclusion criteria.

Informed Consent

1. Are capable of giving informed consent as described in [Appendix 1](#), Section 10.1.3, which includes compliance with the requirements and restrictions listed in the ICF and in this protocol, including the contraception requirements.

Note: For the contraception requirements of this protocol, see [Appendix 4](#). Contraceptive use by men or women should be consistent with local regulations regarding the methods of contraception for those participating in clinical studies.

Patient Characteristics

2. Are male or female patients from 18 to 75 years of age, inclusive, at the time of initial screening (Visit 1).

Note: Women of child-bearing potential (WOCBP) must test negative for pregnancy as indicated by a negative serum pregnancy test at the screening visit followed by a negative urine pregnancy test within 24 hours prior to first exposure to study drug.

3. Have venous access sufficient to allow the protocol-required blood sampling.
4. Are willing and able to complete the scheduled study assessments, including endoscopies and daily diary entries.

Disease-Specific Characteristics

5. Have had an established diagnosis of UC of ≥ 3 months in duration before baseline (Visit 2), which includes endoscopic evidence of UC and a histopathology report that supports a diagnosis of UC (see Section 8.1.1.3). Supportive endoscopy and histopathology reports must be available in the source documents.
6. Have moderately to severely active UC as defined by a modified Mayo score (MMS) of 4 to 9 with an endoscopic subscore (ES) ≥ 2 , with endoscopy performed within 14 days before baseline.

Note: The MMS requires accurate documentation of the stool frequency (i.e. baseline prior to onset of UC signs/symptoms OR stool frequency when in remission) as well as

3 days of diary data (of stool frequency and rectal bleeding) in the 7 days preceding the first date of bowel prep, if no bowel prep, day of endoscopy).

Note: The Mayo ES, as determined by the Image Review charter, will be provided to the site prior to randomization to enable determination of the MMS for eligibility.

7. Have evidence of UC extending proximal to the rectum (with ≥ 15 cm of involved colon).
8. Have documentation of
 - 8a. a surveillance colonoscopy (performed according to local standard) within 12 months before baseline for

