8.1. Efficacy Assessments

This study uses components and permutations of the Mayo score¹⁷ to assess UC disease activity for the primary and several secondary endpoints, as defined in the table below.

Complete and accurate daily recording of the Mayo SF and RB subscores by participants in their daily eDiary is necessary for the success of the study. Adequate bowel preparation and an endoscopy with adequate visualization of the mucosa will enable calculation of the Mayo ES.

Endpoint	Definition
Clinical remission	SF subscore = 0, or SF = 1 with a decrease of ≥ 1 point from baseline, and RB subscore = 0, and ES = 0 or 1, excluding friability
Clinical response	A decrease in the MMS of ≥ 2 points and $\geq 30\%$ decrease from baseline, and A decrease of ≥ 1 point in the RB subscore from baseline or a RB score of 0 or 1
Endoscopic remission	Mayo ES = 0 or 1, excluding friability
Endoscopic response	A decrease in the Mayo ES of ≥ 1 point compared to baseline
Symptomatic remission	SF = 0, or SF = 1 with a decrease of ≥ 1 point from baseline, and RB = 0
Symptomatic response	$\geq 30\%$ decrease from baseline in the composite clinical endpoint of the sum of SF and RB subscores
Histologic remission	Geboes score < 2 or Geboes subscores = 0 for Grade 2a, 2b, 3, 4, and 5 (equivalent definitions)
Histologic-endoscopic mucosal healing	Geboes score < 2 AND endoscopic remission

Abbreviations: ES = endoscopic subscore; MMS = modified Mayo score; RB = rectal bleeding; SF = stool frequency.

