Physician’s Global Assessment: The PGA is a physician-reported measure that summarizes the investigator’s assessment of the participant’s UC disease activity on a 4-point scale. Assessment of the PGA score will be collected by the investigator or designee at appropriate study visits and entered into the eCRF. Consistent with regulatory guidance, the PGA will not be used as an efficacy assessment in this study.

Each subscore is scored on a 4-point scale, ranging from 0 to 3, to give a maximum Mayo score of 12. The MMS is a sum of the Mayo SF, RB, and ES, giving a maximum MMS of 9.

Additional scorings involving the Mayo score (for example, CCI [REDACTED] have been described and may be used in analyzing data from this study.

See [Appendix 9](#) for more information about the Mayo score.

See [Appendix 11](#) for more information about the daily electronic diary.

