During exceptional circumstances, some sites might not be able to conduct endoscopies. Gastrointestinal societies have recommended that patients with IBD who do not have COVID-19 should stay on IBD therapies with a goal of sustaining remission.^{33,34} For participants in a clinical study, remaining on an assigned study treatment might be protective against immediate risk of disease worsening or recurrence. Remaining on study treatment might also alleviate stress

for the participant, the healthcare provider, and the medical system insofar as stress is created by withdrawing participants study treatment and then needing to find alternative therapies for the withdrawn participants.

This section of this appendix addresses the retention of participants in the study who, in the opinion of the investigator, could benefit from continuing to receive study treatment, despite their inability to have certain protocol-specified endoscopies. Such participants are referred to herein as “Impacted Patients.”

A determination of clinical response status, as described in Section 8.1 of the protocol, relies upon stool frequency and rectal bleeding data. Therefore, if a participant is found to be noncompliant with their daily diary entry to the extent that an assessment of clinical response status cannot be made, the participant will not be eligible to be regarded as an Impacted Patient.

The investigator or designee must notify the sponsor and make a request to classify a participant as an “Impacted Patient.” However, before doing so, the options for extended visit interval tolerances (wider windows) should be exhausted. Also, other options to enable performing the endoscopy within the allowed timing should be considered, for example, use of an alternate, approved endoscopy site. If, after considering these options, an endoscopy must nevertheless be missed, the investigator or designee must describe in the Impacted Patient’s source documents both the reason for the missed endoscopy and the options which were considered but rejected.

Without data from postbaseline endoscopies, it is not possible to use per protocol criteria to determine the participant’s status as a responder or nonresponder at the end of the Induction Period or to determine a participant’s response to Extension Induction or Extension Maintenance dosing, or to determine clinical response/remission status at Week 52.

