Therefore, when Impacted Patients miss any of the endoscopies after randomization, then, instead of the protocol-defined clinical response definition, a standardized Clinical Benefit criterion will be used for Impacted Patients.

The specific definition of Clinical Benefit for Impacted Patients will be provided separately from the protocol.

Impacted Patients who demonstrate Clinical Benefit at Week 12 will enter the blinded maintenance period. Impacted Patients who do not demonstrate Clinical Benefit at Week 12 will enter the extension induction period.

Impacted Patients who demonstrate Clinical Benefit at the end of the extension induction period will enter the extension maintenance period, whereas those who do not will undergo early discontinuation procedures.

Documentation

Documentation of changes in study content

Changes to study conduct will be documented.

Sites will identify and document the details of how participants, visits types, and conducted activities were affected by exceptional circumstances. Dispensing/shipment records of study intervention and relevant communications, including delegation, should be filed with site study records.

Source documents generated at a location other than the study site should be part of the investigator's source documentation and should be transferred to the site in a secure and timely manner.

Missing data and other protocol deviations

Missing data will be captured as protocol deviations. The study site should document specific explanations for any missing data and other protocol deviations. Although protocol deviations may be unavoidable in an exceptional circumstance, documentation of protocol deviations and missing data will be important for data analysis and reporting.

11. References

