4.1.2.1. Non-Responder Imputation (NRI)

The primary outcome is the proportion of patients with clinical remission at Week 12. For this and other categorical efficacy endpoints (for example, clinical remission (week 52), clinical response (week 12, 52), and endoscopic remission (week 12, 52)), non-responder imputation (NRI) will be used for missing clinical assessment values. Specifically, all patients who discontinue from the study at any time prior to week 12 for any reason or fail to have an adequate week 12 efficacy assessment will be considered a non-responder at week 12. Patients who discontinue from the study for any reason at any time prior to week 52 after having enrolled into the Maintenance Period or fail to have an adequate week 52 efficacy assessment, will be considered a non-responder at week 52.

The NRI may be applied at any time point specified for analysis.

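### A missed endoscopy makes a participant a nonresponder for clinical response even when diary and baseline scores already prove response

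*Protocol*

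**What the plan says.** Protocol 8.1 defines clinical response as a fall in the modified Mayo score (MMS) of at least 2 points and at least 30% from baseline, together with a rectal bleeding (RB) condition: a fall of at least 1 "point in the RB subscore from baseline or a RB score of 0 or 1". Section 8.1.1.2 bounds the components: "Each subscore is scored on a 4-point scale, ranging from 0 to 3". It also gives the total: "The MMS is a sum of the Mayo SF, RB, and ES, giving a maximum MMS of 9".

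Appendix 13, under Missing Endoscopies, says of participants who miss an endoscopy in exceptional circumstances: "Without data from postbaseline endoscopies, it is not possible to use per protocol criteria to determine" responder status after induction, response in the extension periods, or response and remission at Week 52. It then provides that "instead of the protocol-defined clinical response definition, a standardized Clinical Benefit criterion will be used for Impacted Patients". That criterion is to be defined outside the protocol.

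For the analysis, Protocol 9.4.1.2 treats participants with missing clinical efficacy data as nonresponders. SAP 4.1.2.1 says that patients who "fail to have an adequate week 12 efficacy assessment will be considered a non-responder at week 12", and has a matching rule for Week 52. The SAP mentions neither Impacted Patients nor Clinical Benefit. SAP 4.4.1.3 identifies Week 12 responders for the maintenance analyses by their status in the IWRS.

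**The concern.** Clinical response is a threshold on a bounded sum, plus a condition that uses the diary only. A large enough improvement in stool frequency (SF) and RB can pass the threshold even at the worst possible ES. Response is then known, and scoring it as failure is a misclassification that the plan builds in.

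The endpoints at stake are the secondary clinical response endpoints at Weeks 12 and 52. If endoscopies are missed equally often in each arm and response is more frequent on drug, more true responders are lost on drug and the estimated difference shrinks.

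There is also a possible mismatch. A participant could pass Clinical Benefit, enter maintenance and be held in the IWRS as a Week 12 responder, while the Week 12 analysis counts the same participant as a nonresponder.

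**Working it through.** The documents give no figure on this point, so there is none to reproduce. The check is a full enumeration.

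**Inputs**
- SF, RB and ES are whole numbers from 0 to 3 (Protocol 8.1.1.2). SAP Appendix 6 rounds the weekly SF and RB scores to integers.
- Eligible baseline: ES of 2 or 3 and MMS of 4 to 9 (Protocol 5.1, criterion 6).
- Response rule: Protocol 8.1.

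**Formula.** With baseline (SF0, RB0, ES0), MMS0 = SF0 + RB0 + ES0, visit diary (SF1, RB1) and unknown ES = e:

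D(e) = MMS0 − (SF1 + RB1 + e)

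Response if D(e) ≥ 2, D(e)/MMS0 ≥ 0.30, and (RB0 − RB1 ≥ 1 or RB1 ≤ 1).

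D(e) falls as e rises, and the RB condition does not involve e. Response is therefore certain if the rule holds at e = 3, and nonresponse is certain if it fails at e = 0.

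**Two worked cases**
- Baseline SF 3, RB 2, ES 3 (MMS 8); Week 12 SF 1, RB 0. At e = 3 the MMS is 4, so D = 4 (50%), and RB is 0. Response is certain.
- Baseline SF 0, RB 2, ES 3 (MMS 5); Week 12 SF 0, RB 0. At e = 3 the MMS is 3, so D = 2 (40%), and RB is 0. Response is certain.

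**Number of combinations.** There are 4 × 4 × 2 = 32 baseline sets with ES 2 or 3. Four have MMS below 4 (three with ES 2, one with ES 3), leaving 28. With 16 visit diary pairs, 28 × 16 = 448.

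| Status without ES | Combinations | Share |
|---|---|---|
| Response certain | 69 | 15.4% |
| Nonresponse certain | 220 | 49.1% |
| Depends on ES | 159 | 35.5% |

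**Where certain responders lie**
- Baseline MMS 4 to 6: 28 of 304 combinations (9.2%). Baseline MMS 7 to 9: 41 of 144 (28.5%).
- Diaries that meet symptomatic remission: 35 of 44. This is 18 of 27 at baseline MMS 4 to 6 and 17 of 17 at 7 to 9.

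**Sensitivity of the 15.4%**
- If ES cannot be worse than baseline: 95 of 448 (21.2%).
- If neither SF nor RB can be worse than baseline: 67 of 194 (34.5%).

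**Same test for clinical remission.** Remission is certain in 0 of 448, excluded in 404 (90.2%) and dependent on ES in 44 (9.8%). The diary can rule remission out but never confirm it, and NRI agrees whenever it is ruled out.

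**The case against.** **The protocol may mean a measured ES.** Section 8.1.1.3 says the endoscopic score set under the Image Review charter is used for endpoints and responder status. On that reading, no ES means no MMS, and testing the four possible values is an added rule. This is fair as an account of procedure. It does not change the logic: under the Section 8.1 definition, every value the endoscopy could have returned gives the same answer.

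**The mis-scoring is a reading.** The SAP does not define an adequate assessment. Protocol 9.4.1.2 also has a clause about participants not assessed well enough to tell whether they meet the response requirements, which arguably spares someone whose response is already certain. This stands in part. But the same section also names missing clinical efficacy data, and Appendix 13 says status cannot be determined, so a programmer would probably code nonresponse. The rule is at best ambiguous.

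**The affected group is probably small.** Appendix 13 requires exceptional circumstances, exhausted extended windows, other options considered, adequate diaries and a request to the sponsor. The endpoint is secondary and has no multiplicity control, and the error is likely to be towards no effect. All of this stands and sets the severity.

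**Stronger readings that the documents do not support**
- A reader might add 69 and 220 and infer that 64.5% of cases (289 of 448) are mis-scored. But 220 of the 289 (76%) are certain nonresponders, whom NRI scores correctly.
- A reader might take 15.4% as a share of participants. It weights all combinations equally, and the documents give no score distribution.
- A reader might blame Appendix 13 for the mis-scoring. That appendix governs retention and scores nobody; the scoring comes from the NRI text.
- A reader might infer a definite clash with Clinical Benefit. Its definition lies outside the documents, so a clash is only possible.

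**Conclusion.** The point holds, and it is minor. The blanket statement in Appendix 13 is wrong for clinical response, and the NRI rules read literally score some logically certain responders as failures at Weeks 12 and 52. The exposed share is 69 of 448 eligible score combinations (15.4%), concentrated where symptoms have clearly improved.

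The effect on results cannot be sized, because the number of missed endoscopies is not given. For scale, with about 40 placebo participants (Protocol 9.2), one misclassified responder moves that arm's Week 12 rate by 1/40 = 2.5 percentage points.

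The conclusion assumes integer subscores, known baseline scores including the screening ES, adequate diary data and no intercurrent event. The last condition matters: under the composite strategy (Protocol 9.4.1.2, SAP 4.3.2), participants who stop assigned treatment, take prohibited medication or increase mandatory stable medication are nonresponders whatever their scores. The primary endpoint is unaffected.

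**What to change.** 1. In SAP 4.1.2.1, add a rule for clinical response at Weeks 12 and 52. It applies to participants still on assigned treatment, with no composite-strategy intercurrent event, adequate diary data and a missing ES. Derive clinical response with ES set to 0, 1, 2 and 3; if all four results agree, use that result; otherwise apply NRI. State that participants with an intercurrent event remain nonresponders.
2. In Appendix 13, change the statement to say that determination *may not be possible* without a postbaseline endoscopy.
3. Reconcile the Clinical Benefit status in Appendix 13 and the IWRS responder status in SAP 4.4.1.3 with the Section 8.1 clinical response status used in the analysis. How participants are routed is left to the sponsor.

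The cost is one extra derivation rule, a small amount of programming and the wording changes. No new data are needed, and only participants with missed endoscopies are affected.

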6.7. Appendix 7: List of Planned Laboratory Analytes with Reference
Range Sources.....64

7. **References.....68**

Version history

This Statistical Analysis Plan (SAP) for study J1P-MC-KFAH (KFAH) is based on the protocol dated 18Nov2020 and approved prior to unblinding.

Table KFAH.1. SAP Version History Summary

SAP Version	Approval Date	Change	Rationale
1		Not Applicable	Original version

1. Introduction

Study J1P-MC-KFAH is an adaptive Phase 2, randomized, double-blind, placebo-controlled trial of LY3471851 (NKTR-358) in patients with moderately to severely active ulcerative colitis.

There are no changes to the analyses described in the protocol.

1.1. Objectives, Endpoints, and Estimands

Objectives	Endpoints
Primary	

 • To determine whether LY3471851 is superior to placebo in inducing clinical remission at Week 12 in patients with moderately to severely active ulcerative colitis (UC) 	
 • The difference in the proportion of participants who achieve clinical remission based on MMS at Week 12 without permanently discontinuing treatment
Secondary	

 • To evaluate the efficacy of induction treatment with LY3471851 compared to placebo with respect to clinical, endoscopic, and histologic improvement 	
 • The difference between LY3471851 and placebo in the proportion of participants who have not permanently discontinued at Week 12 and have achieved at Week 12: 
 ○ clinical response ○ endoscopic remission ○ endoscopic response ○ symptomatic remission ○ symptomatic response ○ histologic remission ○ histologic-endoscopic mucosal healing

 • To evaluate the efficacy of maintenance treatment with LY3471851 compared to placebo with respect to clinical, 	
 • The difference between LY3471851 and placebo in the proportion of participants who were responders at

endoscopic, and histologic improvement
	
Week 12 (Week 12 Responders) and have not permanently discontinued at Week 52, who at Week 52 still have:
 
 ○ clinical remission ○ clinical response ○ endoscopic remission ○ endoscopic response ○ symptomatic remission ○ symptomatic response ○ histologic remission ○ histologic-endoscopic mucosal healing

 • To evaluate the efficacy of treatment with LY3471851 compared to placebo with respect to patient-reported outcomes and quality of life measures 	
 • Comparison of mean changes from baseline to Week 12 and to Week 52 in scores for 
 ○ IBDQ ○ Urgency NRS ○ Abdominal Pain NRS ○ Nocturnal Stools ○ Bristol Stool Scale ○ PGR-S ○ Fatigue NRS

 • To evaluate the PK of LY3471851 	
 • Week 12 LY3471851 trough concentrations

Tertiary/Exploratory
	
	

Abbreviations: CCI [redacted]; IBDQ = Inflammatory Bowel Disease Questionnaire; MMS = modified Mayo score, NRS = numeric rating scale; PGR-S = Patient's Global Rating of Severity; PK = pharmacokinetics; UC = ulcerative colitis; CCI [redacted].

Primary estimand

The primary clinical question of interest is: What is the intervention difference in successful response rate of clinical remission based on MMS at Week 12 of intervention in patients with moderately to severely active UC, where successful response is defined as patient who achieves clinical remission without discontinuing treatment, without increasing mandatory stable medications, and without taking prohibited medications prior to the time point of interest? The primary comparison will be assessed using a composite estimand strategy to address the intercurrent events.

The estimand is described by the following attributes:

Population: patients with moderately to severely active UC. Further details can be found in Section 3.

Endpoint: clinical remission based on MMS at Week 12 in MMS.

Treatment condition: the randomized treatment without rescue medication or change in background medication (treatment policy strategy). Further details on study interventions and concomitant, including rescue, interventions can be found in Section 6.

The 2 intercurrent events “intervention discontinuation for any reason” and “initiation of rescue intervention or change in background intervention” are both addressed by the treatment condition of interest attribute. There are no remaining intercurrent events.

Population-level summary: difference in proportion of participants achieving clinical remission at Week 12 between intervention conditions.

Rationale for estimand: The data collected after the treatment discontinuation or post-rescue medication will be categorized as nonresponder.

Secondary estimands

- 1) Clinical response / endoscopic remission / endoscopic response / symptomatic remission / symptomatic response / histologic remission / histologic-endoscopic mucosal healing at Week 12

The secondary clinical question of interest is: What is the intervention difference in successful response rate of clinical response / endoscopic remission / endoscopic response / symptomatic remission / symptomatic response / histologic remission / histologic-endoscopic mucosal healing at Week 12 of intervention in patients with moderately to severely active UC, where successful response is defined as patient who achieves clinical response / endoscopic remission / endoscopic response / symptomatic remission / symptomatic response / histologic remission / histologic-endoscopic mucosal healing without discontinuing treatment, without increasing mandatory stable medications, and without taking prohibited medications prior to the time point of interest? The secondary comparisons will be assessed using a composite estimand strategy to address the intercurrent events.

The estimand is described by the following attributes:

Population: patients with moderately to severely active UC who have not permanently discontinued at Week 12 and have achieved at Week 12. Further details can be found in Section 3.

Endpoint: clinical response / endoscopic remission / endoscopic response / symptomatic remission / symptomatic response / histologic remission / histologic-endoscopic mucosal healing at Week 12.

Treatment condition: the randomized treatment without rescue medication or change in background medication (treatment policy strategy). Further details on study interventions and concomitant, including rescue, interventions can be found in Section 6.

The 2 intercurrent events “intervention discontinuation for any reason” and “initiation of rescue intervention or change in background intervention “ are both addressed by the treatment condition of interest attribute. There are no remaining intercurrent events.

Population-level summary: difference in proportion of participants achieving clinical response / endoscopic remission / endoscopic response / symptomatic remission / symptomatic response / histologic remission / histologic-endoscopic mucosal healing at Week 12 between intervention conditions.

Rationale for estimand: The data collected after the treatment discontinuation or post-rescue medication will be categorized as nonresponder.

- 2) Clinical remission / clinical response / endoscopic remission / endoscopic response / symptomatic remission / symptomatic response / histologic remission / histologic-endoscopic mucosal healing at Week 52

The secondary clinical question of interest is: What is the intervention difference in successful response rate of clinical response / endoscopic remission / endoscopic response / symptomatic remission / symptomatic response / histologic remission / histologic-endoscopic mucosal healing at Week 52 of intervention in patients with moderately to severely active UC, where successful response is defined as patient who achieves clinical response / endoscopic remission / endoscopic response / symptomatic remission / symptomatic response / histologic remission / histologic-endoscopic mucosal healing without discontinuing treatment, without increasing mandatory stable medications, and without taking prohibited medications prior to the time point of interest?

The estimand is described by the following attributes:

Population: patients with moderately to severely active UC who were responders at Week 12, have not permanently discontinued at Week 52, have achieved at Week 52. Further details can be found in Section 3.

Endpoint: clinical remission / clinical response / endoscopic remission / endoscopic response / symptomatic remission / symptomatic response / histologic remission / histologic-endoscopic mucosal healing at Week 52.

Treatment condition: the randomized treatment without rescue medication or change in background medication (treatment policy strategy). Further details on study interventions and concomitant, including rescue, interventions can be found in Section 6.

The 2 intercurrent events “intervention discontinuation for any reason” and “initiation of rescue intervention or change in background intervention “ are both addressed by the treatment condition of interest attribute. There are no remaining intercurrent events.

Population-level summary: difference in percentage of participants achieving clinical remission / clinical response / endoscopic remission / endoscopic response / symptomatic remission / symptomatic response / histologic remission / histologic-endoscopic mucosal healing at Week 52 between intervention conditions.

Rationale for estimand: The data collected after the treatment discontinuation or post-rescue medication will be categorized as nonresponder.

3) IBDQ / Urgency NRS / Abdominal Pain NRS / Nocturnal Stools / Bristol Stool Scale / PGR-S / Fatigue NRS

The secondary clinical question of interest is: What is the intervention difference in IBDQ / Urgency NRS / Abdominal Pain NRS / Nocturnal Stools / Bristol Stool Scale / PGR-S / Fatigue NRS at Week 12 and Week 52 of intervention in patients with moderately to severely active UC regardless of intervention discontinuation for any reason and regardless of initiation of rescue intervention or change in background intervention?

The estimand is described by the following attributes:

Population: patients with moderately to severely active UC. Further details can be found in Section 3.

Endpoint: IBDQ / Urgency NRS / Abdominal Pain NRS / Nocturnal Stools / Bristol Stool Scale / PGR-S / Fatigue NRS at Week 12 and Week 52.

Treatment condition: the randomized treatment without rescue medication or change in background medication (treatment policy strategy). Further details on study interventions and concomitant, including rescue, interventions can be found in Section 6.

The 2 intercurrent events “intervention discontinuation for any reason” and “initiation of rescue intervention or change in background intervention “ are both addressed by the treatment condition of interest attribute. There are no remaining intercurrent events.

Population-level summary: difference in mean change in IBDQ / Urgency NRS / Abdominal Pain NRS / Nocturnal Stools / Bristol Stool Scale / PGR-S / Fatigue NRS at Week 12 and Week 52 between intervention conditions.

Rationale for estimand: The data collected after the treatment discontinuation or post-rescue medication will not represent the true efficacy effects.

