4.4.1.2. Secondary Efficacy Endpoints for the Induction Period

Secondary efficacy endpoints for the induction dosing period for participants who have not permanently discontinued at Week 12 and have achieved at Week 12 include clinical response, endoscopic remission, endoscopic response, symptomatic remission, symptomatic response, histologic remission, and histologic-endoscopic mucosal healing at Week 12.

Analyses will be performed as per the methodology described in Section 4.1.1.

The mITT population will be used for the secondary efficacy outcome analyses.

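### The SAP's binary secondary estimands put non-discontinuation and achieving the endpoint into the Population, which contradicts the composite strategy, the NRI rule and the mITT analysis set

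*SAP*

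**What the plan says.** **Where the restriction appears**

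- SAP 1.1, secondary estimand 1 (seven Week 12 binary endpoints): the Population attribute is limited to UC patients "who have not permanently discontinued at Week 12 and have achieved at Week 12".
- SAP 1.1, secondary estimand 2 (eight Week 52 binary endpoints): patients "who were responders at Week 12, have not permanently discontinued at Week 52, have achieved at Week 52".
- SAP 4.4.1.2 introduces the Week 12 endpoints as being "for participants who have not permanently discontinued at Week 12 and have achieved at Week 12 include clinical response" and the rest of the list. SAP 4.4.1.3 does the same for Week 52. Both sections then name mITT as the analysis set and send the reader to Section 4.1.1 for methods.

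**What points the other way**

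- Estimand 1 itself: "The secondary comparisons will be assessed using a composite estimand strategy to address the intercurrent events". For both estimands, success means reaching the endpoint with no treatment discontinuation, no increase in the medications that must stay stable and no prohibited medication. Both give the rationale "The data collected after the treatment discontinuation or post-rescue medication will be categorized as nonresponder".
- SAP 4.1.2.1 counts as nonresponders "all patients who discontinue from the study at any time prior to week 12 for any reason", together with anyone lacking an adequate Week 12 assessment. It covers the other categorical efficacy endpoints and has a parallel rule for Week 52.
- Protocol 9.4.1.2 treats a participant whose intercurrent event leads to permanent discontinuation as a failure from then on.
- The primary estimand and the continuous secondary estimand carry no restriction: "Population: patients with moderately to severely active UC. Further details can be found in Section 3".

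**The concern.** The Population attribute fixes the denominator. Non-discontinuation and achieving the endpoint are outcomes observed after randomisation, and under a composite strategy they belong in the definition of success. A patient who discontinues cannot be both outside the population and a nonresponder within it, yet estimand 1 says both.

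At stake is the denominator of fifteen secondary comparisons (seven at Week 12, eight at Week 52). As written, the SAP supports two denominators. One conditions on a post-randomisation event, so it no longer compares the arms as randomised.

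**Working it through.** **Inputs.** The documents give no expected rate for any secondary endpoint and no discontinuation rate, so there is no plan figure to reproduce on this point. For illustration I borrow the planning values for the primary endpoint (SAP Section 5: about 5% placebo, 35% active; placebo n = 40, largest active arm n = 80) and treat them as NRI rates. The discontinuation proportions d are assumptions.

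**Step 1: denominator under mITT with NRI.** Expected responders are 80 × 0.35 = 28 and 40 × 0.05 = 2. The rates are 28/80 = 35.0% and 2/40 = 5.0%, a difference of 30.0 points.

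**Step 2: the Population line taken literally.** Only those who achieved the endpoint remain, so the rates are 28/28 = 100% and 2/2 = 100%. The difference is 0 whatever the data.

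**Step 3: only the non-discontinuation half applied.** Under the composite rule all discontinuers are nonresponders, so the numerator is unchanged and the denominator falls from n to n(1 − d). An NRI rate r becomes r/(1 − d). The multiplier runs from 1/0.95 = 1.05 to 1/0.70 = 1.43. With equal d in both arms:

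| d | Active 0.35/(1−d) | Placebo 0.05/(1−d) | Difference (points) |
|---|---|---|---|
| 0 | 35.0% | 5.0% | 30.0 |
| 5% | 36.8% | 5.3% | 31.6 |
| 10% | 38.9% | 5.6% | 33.3 |
| 20% | 43.8% | 6.3% | 37.5 |
| 30% | 50.0% | 7.1% | 42.9 |

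**Step 4: unequal discontinuation.** Write c for a completer rate, so that the NRI rate is c(1 − d). The completer difference minus the NRI difference is then c_A·d_A − c_P·d_P (A active, P placebo), which can take either sign.

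- Equal NRI rates of 20%, d = 10% placebo and 30% active: 0.20/0.70 − 0.20/0.90 = 0.286 − 0.222 = +6.3 points where the NRI difference is 0. Swapping the two d values gives −6.3.
- Completer rates of 50% active and 30% placebo (difference 20 points), d = 20% active and 10% placebo: the NRI difference is 0.50 × 0.80 − 0.30 × 0.90 = 13 points, so the completer figure is 7 points more favourable.
- The same completer rates with d swapped: 0.50 × 0.90 − 0.30 × 0.80 = 21 points, so the completer figure is 1 point less favourable.

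**Step 5: the texts side by side.** In Protocol Section 3 and the SAP 1.1 objectives table, the Week 12 phrase follows a reference to the proportion of participants, so there it defines the numerator. The corresponding Week 52 sentence is looser and could be read either way, but the same protocol entry prescribes the composite estimand. SAP Section 1 says the protocol's analyses are unchanged, so no new population was declared.

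**The case against.** The strongest reply is that the operative rule is clear elsewhere. Estimand 1 poses its question in patients with active UC, puts non-discontinuation in the success definition and names the composite strategy. NRI extends to these endpoints, and Sections 4.4.1.2 and 4.4.1.3 name mITT. A programmer following the analysis set and the imputation rule has one denominator. The literal reading gives 100% everywhere and would be noticed at once. The SAP nowhere sets out a completer analysis. These are also secondary endpoints in a Phase 2 trial without multiplicity control.

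Much of this stands: the wording looks like an endpoint phrase pasted into the wrong attribute, and it does harm only if followed. It does not remove the conflict. The restriction sits in four places, two of them in the analysis sections. Those two refer only to Section 4.1.1, where percentages use non-missing observations as the denominator, and that does not settle whether discontinuers are counted. The SAP does not say which text prevails.

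A reader might infer more than the documents support:

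- **That the plan inflates the treatment effect.** The full wording gives a difference of 0, and under the completer reading the direction depends on discontinuation rates that the documents do not give.
- **That limiting Week 52 to Week 12 Responders is part of the error.** Protocol Section 3 plans that restriction, and Week 12 Nonresponders, placebo patients included, receive LY3471851 from Week 14 (Protocol 4.1).

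**Conclusion.** The point holds as an internal contradiction that should be corrected. The Population attributes of both binary secondary estimands, and the matching text in SAP 4.4.1.2 and 4.4.1.3, give a wrong denominator if followed: either 100% response in every arm, or a completer analysis with each rate multiplied by 1/(1 − d).

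The identity in Step 2 and the multiplier in Step 3 need no assumption beyond the composite rule. Every figure in points rests on assumed rates and shows only what could happen, so none should be quoted as the expected bias. The primary estimand and the continuous secondary estimand are not affected.

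**What to change.** 1. **Week 12** (SAP 1.1 estimand 1; 4.4.1.2): set the Population to mITT.
2. **Week 52** (SAP 1.1 estimand 2; 4.4.1.3): set the Population to mITT participants who were Week 12 Responders. Do not widen it to all mITT participants.
3. **Success definition:** leave all the conditions in the response definition, as both estimands already word it. The endpoint is achieved without discontinuing treatment, without increasing mandatory stable medications and without taking prohibited medications. The two medication conditions must not be lost in the edit.
4. **Sections 4.4.1.2 and 4.4.1.3:** remove the restricting clause and state that NRI (Section 4.1.2.1) applies, with every participant in the stated population in the denominator. Section 4.3.2 already links NRI to these intercurrent events for the primary endpoint and can serve as the model.

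The cost is SAP wording only. Data collection, sample size and the primary analysis do not change. The edit should be made before unblinding.
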